To assess the efficacy of custom-manufactured compression hosiery compared to off-the-rack compression hosiery for improving patient satisfaction and compliance with prescribed compression therapy.

- 1) Health-Related Quality of Life (HRQoL): We will use the short-form 12-item (SF12) HRQoL instrument for measuring HRQoL. It has been used widely and validated in many health conditions, and can be administered to patients in less than 5 minutes. It produces overall HRQoL estimates and subscale scores that assess both mental / emotional and physical functioning related to health.

2) Five-point satisfaction scale: This scale is used to assess the patient's pain management experience during their postoperative care. It consists of patients rating their overall postoperative pain management experience using a 5-point rating system. The scale ranges from 1 to 5, with 1 being "extremely dissatisfied", 2 "somewhat dissatisfied", 3 "Neutral/Neither satisfied nor dissatisfied", 4 "somewhat satisfied" and 5 "extremely satisfied" with their postoperative pain care. This rating has been used in other clinical trials and has been shown to be a reproducible assessment tool.

3) Brief Pain Inventory: The Brief Pain Inventory is a medical questionnaire used to measure pain, developed by the Pain Research Group of the WHO Collaborating Centre for Symptom Evaluation in Cancer Care.^{1,2}

Primary outcome measures

HRQoL, BPI and 5-point satisfaction scale will be assessed at baseline, at clinical follow-up at 90 days. Additionally, the BPI will also be administered via phone at 6 weeks.

Compliance with stocking use will be measured by a daily diary entry and will be the accumulated total of hours worn over 90 days.

H. SECONDARY OBJECTIVES

- To identify subgroups that may benefit more from custom hosiery.
- To determine whether improved fit affects likelihood to progress to invasive treatment.

Secondary outcome measures

- The sample size (200 subjects) will allow us to investigate subgroup effects. Preliminary a priori hypotheses are that patients with difficult to fit legs (eg., large calf/ankle ratio) will have significant improvements in compliance and satisfaction with custom fit hosiery.
- Progression to ablation therapy will be determined by patient preference for further intervention. We will measure efficacy as a simple proportion between the randomized groups.

IX. STUDY POPULATION

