clinical trial with a 2-arm parallel-group design to assess the efficacy of custom-fitted compression hosiery vs off-the-rack compression hosiery.

The custom stockings take 2 weeks to manufacture. In order to maintain the blind, stockings will be procured by the UT CV Surgery purchasing personnel and distributed to the subjects in unmarked packaging within three weeks of randomization. Neither the prescribing physician nor the patient will know the treatment assignment.

Screened patients meeting the eligibility criteria will have a below-knee laser measurement scan, and will be randomized into one of the two study groups.

At the screening visit, patients will be evaluated for trial eligibility and the study will be explained. For eligible patients who wish to participate, informed consent will be obtained and the patient will receive history and physical exam and will complete baseline HRQoL and pain scale surveys. Volumetric scans will be performed and the data will be stored. Patients will be randomized by a study coordinator, and will be instructed to expect stockings in the mail within 3 weeks.

After stockings are dispensed, patient should call the office to inform the study nurse or coordinator of the day they are beginning therapy, and biweekly log will be kept as a measure of compliance.

Patients in the study should also complete the Brief Pain Inventory (BPI) before randomization (at baseline following enrollment), by phone during week six, and at clinical follow-up after completing 90 days of compression therapy. Additionally, patients will be assessed on their satisfaction at week six and at 90-day clinical follow-up. This

will be done using the 5-point satisfaction scale with 1 being “very dissatisfied” to 5 being “very satisfied”. The SF-12 HRQoL instrument will also be completed at enrollment, at six weeks and at 90-day follow-up. This will conclude the 90-day treatment period. Patients will be re-contacted at six months post-treatment to determine whether they are still using their stockings (or have replaced them) or have progressed to invasive treatment. After the six-month assessment, the study will be concluded and enrollment will be terminated.

Study Conduct

1. Screening

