The PI and research staff will assess patients as possible candidates for enrollment based on the inclusion criteria described previously. A member of the research team - the PI, a Co-investigator, research coordinator, or research nurse will obtain the consent from interested patients who met the preliminary inclusion criteria. The consent process will take place during the clinic visit. Patients will be given adequate time and education about their condition to ask questions about the protocol and research study. Those who wish to participate will be informed they are responsible for the cost of the hosiery as it may not be covered by insurance (most plans do not cover stockings even though they are required prior to preauthorization for ablation therapy). Patients would be responsible for this cost whether or not they are enrolled in the trial – no additional cost to the patient will result from trial participation. The preoperative baseline pain level, using BPI and HRQoL will be recorded at this time. A copy of the signed informed consent shall be provided to the patient, a copy will be

placed in the patient's hospital chart, and a copy will be kept by the research team. Medical/surgical history, vital signs measurements, and standard clinical testing will also be performed as per the usual practice for assessment and management of CEAP class 2-5 venous disease.

2. Quality of life assessment - Brief Pain Inventory

The impact of pain on patient's quality of life will be assessed through a brief pain inventory (BPI) that should be done at enrollment, at the six week point during compression therapy and at the final clinic visit after 90 days of treatment. The BPI will be presented as an easy to comprehend questionnaire for the patients to quantify and communicate their pain experience and how it is affecting their life. It is designed such that patients with 6th-grade education should be able to complete the questionnaire on their own. Question and answers will be provided in a check-box format. The BPI that will be used on this study will be the short version. Patients with difficulty reading or who are physically unable to complete the questionnaire will be assisted by the research team based on their verbal responses to the BPI questions.

3. Enrollment

After screening for eligibility, if all inclusion/exclusion criteria are met and the patient has consented; the patient will be enrolled in the trial.

4. Randomization and Allocation Concealment

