Patients enrolled in the trial will be instructed to report any unwanted effect at any time during the study. For this study, only adverse events that are directly related to the use of compression stocking will be reported. Expected adverse effects of compression therapy will be described to the patients during the screening/enrollment as well as in the informed consent process. Most adverse side effects are minor and may include rash, contact dermatitis, discomfort, lack of symptomatic relief, and in rare cases, local skin ischemia and breakdown.

Safety monitoring will include assessment of:

- i. Adverse Effects (AE)
- ii. Vital Signs
- iii. Wound healing status
- iv. Pain
- v. Satisfaction

All parameters will be closely monitored in a continuous manner, as part of our standard clinical care. Any abnormalities found will be promptly assessed and described in the patient's medical records. Patients will be instructed to call the clinic if problems arise, and will also be assessed at clinic visits. If need be, an immediate unscheduled visit shall be arranged if the patient so desires.

The PI will review AEs as they occur, and requirement for changes to the study design or device use will be determined on an ongoing basis. This study does not require a DSMB.

XIV. STATISTICAL ANALYSIS PLAN

A. Primary Outcomes

The trajectory of BPI, HRQoL and Patient Satisfaction scores at 45 and 90 days of treatment will be measured by mixed-effects linear models between the groups.

Appropriate score transformations will be performed as necessary to meet distributional assumptions of the tests. Randomization is expected to balance the groups with respect to pre-intervention risk factors.

Total time worn over 90 days as reflected in diary entries will be compared by Wilcoxon rank-sum test between the two groups..

A. Secondary Outcomes

[figure not shown]
Additional analyses will be performed to determine whether patient characteristics such as calf/ankle ratio and other measurements made using laser scan data show differential (interaction) effects in the custom-stocking group vs the off-the-rack group.

Progression to ablation will be measured as simple test of proportions (Fisher's Exact test) of those seeking ablative therapy in the custom vs OTR groups.

B. Sample Size Determination

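### The SAP does not say how baseline BPI and SF-12 enter the primary mixed models or which contrast is tested; a baseline-adjusted, pre-named contrast would be more precise at no data cost

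*Combined protocol and SAP*

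**What the plan says.** Section XIV (Statistical Analysis Plan, Primary Outcomes) gives the analysis of the three scores in a single sentence: "The trajectory of BPI, HRQoL and Patient Satisfaction scores at 45 and 90 days of treatment will be measured by mixed-effects linear models". It lists no covariates, does not count baseline among the model's time points, and does not say whether the test is at day 90, averaged over visits, or on group-by-time. The only remark on pre-treatment differences is "Randomization is expected to balance the groups with respect to pre-intervention risk factors".

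Baseline values exist for two of the three scores. Section XII (Study Design/Methodology) says that at the screening visit patients "will complete baseline HRQoL and pain scale surveys", and that they "complete the Brief Pain Inventory (BPI) before randomization (at baseline following enrollment), by phone during week six". Its Screening item says that baseline pain "using BPI and HRQoL will be recorded at this time".

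The Sample Size Determination text frames the detectable difference as a proportion of patients whose quality of life changes after treatment. That uses baseline as a reference but does not describe the mixed model.

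The schedule is stated in two ways. Under Primary outcome measures: "HRQoL, BPI and 5-point satisfaction scale will be assessed at baseline, at clinical follow-up at 90 days", with only BPI added at six weeks. In section XII the SF-12 "instrument will also be completed at enrollment, at six weeks and at 90-day follow-up", and "patients will be assessed on their satisfaction at week six and at 90-day clinical follow-up", with no baseline satisfaction mentioned. The follow-up list in section XII has a six-week telephone questionnaire but names no instrument.

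**The concern.** Several different analyses fit the one sentence: a day-90 difference, a group effect averaged over both visits, a slope difference between days 45 and 90, or, if baseline is treated as a repeated response, a group-by-time interaction that behaves like a change score. Each could be run with or without baseline. They differ in precision and, for the slope, in the question answered.

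Two things are at stake. First, a value already collected could narrow the interval for BPI and SF-12, and nothing commits the analysis to using it. Second, while the baseline handling and the contrast are open, both can be settled after the data are seen. Satisfaction is outside the precision argument unless a baseline is in fact taken. Compliance is outside it because it has its own named test.

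**Working it through.** **The plan's own figure.** The documents give no power or precision figure for the mixed models. The 200 patients come from a binary calculation on improvement in quality of life, which cannot be carried over to a comparison of mean scores. Only the 100 per arm is used here.

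**Inputs.** From the documents: 100 per arm; visits at baseline, about day 45 (taken to be the six-week contact) and day 90. Assumed, because the documents give none of them: unit SD, correlation rho of 0.3, 0.5 or 0.7 equal between all visits, complete data, two-sided 5%, true effect 0.35 SD.

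**Step 1: variance factors.** The variance of the group difference is (2/100) × f, where f depends on the analysis:

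| Analysis | Day 90 | Average of days 45 and 90 |
|---|---|---|
| Unadjusted | 1 | (1 + rho)/2 |
| Change score | 2(1 − rho) | 1.5(1 − rho) |
| Baseline-adjusted | 1 − rho² | (1 + rho)/2 − rho² |

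In both columns unadjusted minus adjusted is rho², and change score minus adjusted is (1 − rho)². Both are positive for rho strictly between 0 and 1, so adjustment is more precise than either alternative. The cost is one degree of freedom.

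**Step 2: interval width at day 90.** Adjusted over unadjusted is √(1 − rho²) = 0.954, 0.866, 0.714, so 5%, 13% and 29% narrower. This needs no effect size.

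**Step 3: power.** Noncentral t with noncentrality d × √(50/f), on 198 degrees of freedom (197 adjusted). For example, day 90, rho 0.5, adjusted: 0.35 × √(50/0.75) = 2.86, giving 81%.

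| 0.35 SD | rho 0.3 | rho 0.5 | rho 0.7 |
|---|---|---|---|
| Day 90, unadjusted | 69% | 69% | 69% |
| Day 90, change score | 55% | 69% | 89% |
| Day 90, adjusted | 73% | 81% | 93% |
| Average, unadjusted | 86% | 81% | 76% |
| Average, change score | 67% | 81% | 96% |
| Average, adjusted | 91% | 94% | 98% |

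The average rows assume 0.35 SD at both visits. At day 90 the gain is 4, 12 and 24 points over unadjusted, and 18, 12 and 4 points over change score. With unequal correlations (0.5 baseline to day 45, 0.4 baseline to day 90, 0.7 between follow-up visits), simulated day-90 power rises from 69% to 76%.

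**Step 4: does adding baseline as a response settle it?** Only in part. In an unconstrained group-by-visit model with baseline as a response, the day-90 group difference is still the raw day-90 difference, and the interaction is the change-score difference. One simulated data set fitted with a random intercept gave 0.485 and 0.362, equal to the raw and change-score differences. The adjusted precision comes from a baseline covariate or from constraining baseline means to be equal across arms.

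**Step 5: the slope from day 45 to day 90.** Its variance factor is 2(1 − rho). If the effect is equal at both visits, the slope difference is zero and power is 5%. If the effect grows from 0.175 to 0.35 SD, power is 18%, 23% and 36%, against 73%, 81% and 93% for the adjusted day-90 contrast.

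**Step 6: type I error.** Each test taken alone rejects in 4.6% to 5.3% of simulated null trials. Taking the smallest p-value gives about 9% to 10% across the three versions of the day-90 test (unadjusted, change, adjusted), about 11% across the three unadjusted contrasts, and 16% to 18% across all the listed versions.

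**The case against.** The strongest reply is that the sentence is brief, not wrong. Trajectory may be meant to include baseline, and the sample-size text, which counts patients whose quality of life changes, points the same way for SF-12. If baseline is a response with means constrained equal across arms, the model already has the adjusted precision. The remark on randomisation concerns risk factors and is not a decision to discard baseline scores. All of this stands. A reader might infer that the plan commits to an unadjusted analysis; the text is silent and does not support that. But no section states a constraint, a covariate or a contrast, so the choice remains open.

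A second reply is that the gain depends on the comparator and on assumptions. This also stands. At rho 0.7 and 0.25 SD, adjustment gains 27 points over an unadjusted day-90 test but only 7 over a change score. At low rho the order reverses. Quoting only the gain over an unadjusted analysis would overstate the case if a change-type analysis is intended.

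A third is that the averaged contrast may not exist for SF-12. If the schedule under Primary outcome measures governs, SF-12 has no six-week value, and the average rows above apply to BPI alone.

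**Conclusion.** The point holds as an improvement that needs no new data, and the plan should adopt it. The omission is certain on the text. The size of the gain is illustrative: at day 90 and 0.35 SD, about 4 to 24 points of power over an unadjusted test and 18 to 4 points over a change score as rho goes from 0.3 to 0.7, given 100 per arm, complete data and equal correlations. Naming the contrast matters at least as much, since a slope test over days 45 to 90 would miss a benefit already present by day 45.

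Two stronger readings are not supported. One is that leaving out baseline would bias the comparison or make it invalid: under randomisation, any single pre-chosen version is unbiased and holds its 5% level. The other is that type I error is inflated by the plan as written: the 9% to 18% arises only if the version is picked after the data are seen, which the open wording permits but does not prescribe.

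The disagreement between the two assessment schedules is real but secondary.

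**What to change.** In section XIV, for BPI and SF-12:

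- include the baseline value of the same score as a covariate, or include baseline as a response with means constrained equal across arms;
- fit visit as categorical with a group-by-visit term;
- name one post-baseline between-group contrast: day 90, or the average of both visits only where a six-week value is collected. The choice is the sponsor's, but it should not be the slope from day 45 to day 90 alone.

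Separately, reconcile Primary outcome measures with section XII on whether SF-12 and satisfaction are taken at six weeks and whether satisfaction has a baseline. Use a baseline term for satisfaction only if one is collected.

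The cost is a few sentences of SAP wording, two schedule statements brought into line, and one degree of freedom per baseline term. The wording should be fixed before the outcome data are seen.

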C. A sample size of 200 (100 per arm) patients would allow for detection of a difference as small as 20% in the proportion of patients with a post-treatment change in QOL. . This detection threshold assumes that 30% of the controls experience some positive change in HRQoL and 40% of the custom group experience improvement. Larger

differences can be detected with a much smaller sample size, but a larger sample will allow us to investigate predictors of improvement such as measurements and patient characteristics.³ The relationship between sample size and proportion of successes in the custom group is shown in the figure below.

Laser-measuring all subjects (not just those randomized to Custom) will allow us to investigate the influence of leg size and shape on likelihood to see improvement in HRQoL and satisfaction, and to identify a variety of other patient-specific factors that predict improvements in outcome. Understanding these relationships may allow us to tailor therapy towards optimization of predicted outcome, and could, for example, help identify a subset of patients for whom progression to ablation therapy may not be necessary.

XV. ETHICS

A. Informed Consent Process

All eligible patients who meet the inclusion criteria will be consented, if willing, after an in-depth description of the study, the study device and potential adverse effects, the risks and benefits, follow-up routine, enrollment and termination processes. The importance of follow-up will be emphasized; however, the patient will retain the right to voluntarily withdraw from the study at any point. It will also be stressed that patient confidentiality will be kept at all times during study through de-identification of data.

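### The sample-size statement claims a 20% detectable difference but rests it on 30% vs 40%; 100 per arm has about 32% power for those rates and fits a 20-point difference instead.

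*Combined protocol and SAP*

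**What the plan says.** Section XIV, Sample Size Determination, sets the trial at 100 patients in each arm, 200 in all, and claims that this number "would allow for detection of a difference as small as 20% in the proportion of patients with a post-treatment change in QOL". It continues: "This detection threshold assumes that 30% of the controls experience some positive change in HRQoL and 40% of the custom group experience improvement". It then says that larger differences need far fewer patients and that the chosen size leaves room to study predictors of improvement. It refers to a plot for the rest: "The relationship between sample size and proportion of successes in the custom group is shown in the figure below". That plot is not in the text available for this review. The text itself gives no alpha, sidedness, power or dropout allowance for this calculation.

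Section XIV.A, Primary Outcomes, plans different analyses: "The trajectory of BPI, HRQoL and Patient Satisfaction scores at 45 and 90 days of treatment will be measured by mixed-effects linear models", and for compliance, "Total time worn over 90 days as reflected in diary entries will be compared by Wilcoxon rank-sum test". The only test of proportions named in section XIV is Fisher's exact test, and it is for progression to ablation.

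**The concern.** The second sentence is offered as the basis for the threshold in the first, but 30% vs 40% is not a 20% difference on either scale. The absolute difference is 10 points. The relative increase is 33%, and a 20% relative increase would be 30% to 36%.

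This paragraph is the only power justification for 200 patients in the available text. A reader who trusts the stated rates would think the trial is powered for 30% vs 40%, and a null result could then be misread as evidence of no benefit. Section XIX commits to publishing whatever the outcome, so the result will be read against this statement. The argument that the sample has room to spare for predictor analyses also fails if 10 points is the real target.

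A linked gap is that the calculation concerns the proportion who improve. Section XIV.A analyses HRQoL as scores and specifies no between-group test of that proportion, so no planned primary analysis has a stated detectable effect.

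**Working it through.** **Inputs from the plan:** n = 100 per arm, 1:1 allocation; stated threshold 20%; control rate 30%; custom rate 40%.

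**Assumptions made here:** two-sided alpha 0.05, no dropout, and a pooled-variance two-proportion test, with Fisher's exact test by enumeration as a check.

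**Step 1. The stated difference.** 40% − 30% = 10 points. 10/30 = 33% relative. 30% × 1.20 = 36%. None of these matches a 20% threshold with rates of 30% and 40%.

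**Step 2. Power at 100 per arm.** With p̄ the mean of the two rates,

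power = Φ{ [ |p₂ − p₁|√n − 1.960 √(2p̄(1 − p̄)) ] / √( p₁(1 − p₁) + p₂(1 − p₂) ) }

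- 30% vs 40%: (0.10 × 10 − 1.960 × √0.455) / √0.45 = (1 − 1.322)/0.671 = −0.48, so power is 31.6%.
- 30% vs 50%: (0.20 × 10 − 1.960 × √0.48) / √0.46 = (2 − 1.358)/0.678 = 0.947, so power is 82.8%.
- 20% vs 40%: (0.20 × 10 − 1.960 × √0.42) / √0.40 = (2 − 1.270)/0.632 = 1.154, so power is 87.6%.

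**Step 3. Patients needed per arm for 80% power.**

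n = [1.960 √(2p̄(1 − p̄)) + 0.842 √( p₁(1 − p₁) + p₂(1 − p₂) )]² / (p₂ − p₁)²

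- 30% vs 40%: (1.322 + 0.565)²/0.01 = 355.9, so 356.
- 30% vs 50%: (1.358 + 0.571)²/0.04 = 93.0, so 93.
- 20% vs 40%: (1.270 + 0.532)²/0.04 = 81.2, so 82.

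**Step 4. Summary, with an assumed 15% loss (85 per arm) alongside.**

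| Rates | Pooled, 100/arm | Fisher, 100/arm | Pooled, 85/arm | Fisher, 85/arm | n/arm for 80% (pooled) |
|---|---|---|---|---|---|
| 30% vs 40% | 31.6% | 26.3% | 27.6% | 22.4% | 356 |
| 30% vs 50% | 82.8% | 79.2% | 76.3% | 71.5% | 93 |
| 20% vs 40% | 87.6% | 84.4% | 81.8% | 77.8% | 82 |

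Power in the table counts the negligible opposite tail.

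**Step 5. Does any other reading rescue 30% vs 40%?**

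- Other alphas: power is 44% at two-sided 0.10 or one-sided 0.05, and 58% at one-sided 0.10. Reaching 80% would need a two-sided alpha of about 0.49.
- 20% as a relative increase (30% vs 36%): power is about 15%.
- 20% as the arcsine effect size h: 2·asin√0.40 − 2·asin√0.30 = 0.21, which is close to 0.20. Power is Φ(0.210 × √50 − 1.960) = Φ(−0.474) = 32%, so the label might be explained but the sample size is not.
- Observing exactly 30/100 vs 40/100: z = 0.10/√(0.35 × 0.65 × 2/100) = 1.48, p = 0.14 (Fisher 0.18). The assumed effect, seen exactly, would not be significant.

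**Step 6. What does 100 per arm fit?** The smallest custom rate detectable against 30% with 80% power is 49.3% (pooled) or 50.2% (Fisher). Over control rates from 10% to 70%, power at 100 per arm is 81% to 95% for a 20-point difference and 29% to 51% for a 10-point difference.

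**Step 7. A guide for the score analysis.** For a single unadjusted two-group comparison of means at 90 days, the detectable difference at 80% power is (1.960 + 0.842) × √(2/100) = 0.40 SD. At 85 per arm it is 2.802 × √(2/85) = 0.43 SD. If alpha were split equally over the four primary outcomes (BPI, HRQoL, satisfaction, hours worn), alpha = 0.05/4 = 0.0125 and the figure is (2.498 + 0.842) × √(2/100) = 0.47 SD at 100 per arm.

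**The case against.** The strongest reply is that this is probably one wrong digit. The 20% threshold and the sample size both fit a 20-point difference, and only the 40% does not. If 50% was meant, the sample size is roughly adequate before dropout and the 32% power never applies. That stands as far as it goes: underpowering is conditional on which rates were intended. It does not remove the error, because the plan as written still states rates for which its own sample size does not work.

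The cited plot may show alpha, power and the intended custom rate. For that reason their absence from the text is not counted against the plan. The plot could settle which number is wrong, but it cannot make the two sentences agree.

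The 32% also refers to a comparison of proportions that section XIV.A does not plan, and an analysis of scores generally uses more information than a split into improved and not improved. This is fair: 32% is not the power of the mixed model. It is, however, the power for the quantity that the plan chose to justify its size. The same mismatch is why a detectable effect on the score scale is needed.

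Finally, the 0.40 SD figure ignores the baseline scores that the trial collects for BPI and SF-12. With an assumed baseline correlation of 0.5, adjustment would reduce it to 0.396 × √(1 − 0.25) = 0.34 SD. It is therefore offered only as a guide, with its conditions stated.

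**Conclusion.** The concern holds. The contradiction between a 20% threshold and rates of 30% and 40% needs no assumption to establish. Its size does: at two-sided 0.05 with 100 per arm and no dropout, power is 31.6% for the stated rates (26.3% by Fisher) and 82.8% for 30% vs 50% (79.2% by Fisher). No usual alpha brings the stated rates near 80%.

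The documents do not show which number is wrong. A slip of 40% for 50% is the likeliest explanation; 20% vs 40%, a true 10-point target, or a 20% taken from the effect size h remain possible. The 15% loss and the four-way alpha split are illustrations, not figures from the plan. Because this is the only power justification in the available text and it is wrong as written, it must be corrected.

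**What to change.** Keep 200 patients and the planned analyses.

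1. Check the original figure, confirm the intended rates, and restate the paragraph so that threshold, rates, test, alpha, sidedness and power agree. Use one test throughout. With the pooled test at two-sided 0.05 and 100 per arm, the wording would be:
   - **If 30% vs 50%:** *83% power for a 20-percentage-point difference; 76% if 15% are lost* (Fisher: 79% and 71%).
   - **If 20% vs 40%:** *88% power for a 20-percentage-point difference; 82% if 15% are lost* (Fisher: 84% and 78%).
   - **If 30% vs 40%:** *about 32% power; the smallest custom rate detectable with 80% power is about 49%; a non-significant result will not be read as no benefit* (Fisher: 26% and 50%).
2. Add an approximate detectable effect for the score comparison: about 0.40 SD at 80% power. Give its conditions: one unadjusted two-group comparison at 90 days, two-sided 0.05, 100 per arm, no adjustment for several primary outcomes. Say that it is a guide and not the power of the 45- and 90-day mixed model. It becomes 0.43 SD at 85 per arm, or 0.47 SD at 100 per arm with alpha split four ways.

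The cost is text only, with no extra patients and no change of analysis. If 30% vs 40% was truly intended, the cost is stating about 32% power openly. Reaching 80% for those rates would take 2 × 356 = 712 patients; that would be a separate decision for the sponsor and is not asked for here.

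### The stated detection threshold is for an undefined HRQoL responder proportion, so it does not apply to the planned score analysis of HRQoL

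*Combined protocol and SAP*

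**What the plan says.** Under Sample Size Determination (section XIV) the plan states: "A sample size of 200 (100 per arm) patients would allow for detection of a difference as small as 20" percent "in the proportion of patients with a post-treatment change in QOL". The supporting assumption is that "30% of the controls experience some positive change in HRQoL" and "40% of the custom group experience improvement". The text then points to a figure of sample size against the proportion of successes in the custom group. That figure is not available in the text under review, but its description is also of a binary outcome.

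Under Primary Outcomes in the same section, HRQoL is handled differently: "The trajectory of BPI, HRQoL and Patient Satisfaction scores at 45 and 90 days of treatment will be measured by mixed-effects linear models". The only test of proportions in the analysis plan is Fisher's exact test, and it is assigned to progression to ablation.

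Section VII names the SF-12 as the HRQoL instrument and says of it: "It produces overall HRQoL estimates and subscale scores that assess both mental / emotional and physical functioning related to health". The primary outcome measures listed there are HRQoL, BPI, satisfaction and hours worn. No HRQoL responder rate is among them. The sample-size text does express exploratory interest in improvement as an outcome ("a larger sample will allow us to investigate predictors of improvement such as measurements and patient characteristics"), without giving a method.

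**The concern.** A sample-size statement tells the reader what the planned primary comparison can and cannot show. Here it is written for one quantity, the share of patients improved, while the plan tests another, the SF-12 score over time. A reader who wants to know whether a null HRQoL result is informative has nothing to use: the plan gives no SD, no target mean difference and no power for the mixed model.

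The responder is also undefined. The SF-12 yields several scores, there is more than one follow-up time, and the wording ranges from a change in QOL, through some positive change, to improvement. If a responder analysis is later carried out because the sample-size text mentions one, its score, cut-off and time point would be chosen after the data are seen. If any rise above zero counted, some patients with no real change would be classed as improved.

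**Working it through.** **Inputs from the plan.** 100 per arm; 30% control and 40% custom improved; a stated detectable difference of 20%. **Assumed, because not stated:** two-sided alpha 0.05, 80% power (90% also shown), dropout 0% to 20%, symmetric measurement error, and 0% to 40% of patients with exactly zero change.

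**1. The plan's own figure.** The usual formula for two proportions, with p̄ the mean of p1 and p2, is

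n per arm = [1.960·√(2p̄(1−p̄)) + 0.842·√(p1(1−p1) + p2(1−p2))]² / (p2−p1)²

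- 30% vs 40%: [1.960·√0.455 + 0.842·√0.450]² / 0.01 ≈ 356 per arm. Power at 100 per arm is 32%.
- 30% vs 50%: [1.960·√0.480 + 0.842·√0.460]² / 0.04 ≈ 93 per arm. Power at 100 per arm is 83%.

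So 200 patients fit a 20-point difference only if the custom rate is 50%, not the stated 40%. That is a separate error. Correcting it would still leave a threshold for a proportion.

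**2. The sized endpoint against the analysed endpoint.**

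| Feature | Sample Size Determination | Primary Outcomes |
|---|---|---|
| Form of outcome | Binary, patient improved or not | Score |
| SF-12 score used | Not named | Not named |
| Minimum change | None given | Not applicable |
| Time point | Post-treatment, day not given | 45 and 90 days |
| Between-arm method | None specified | Mixed-effects linear model |

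No planned between-arm comparison uses the quantity in the first column.

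**3. Sensitivity of the planned score analysis, approximated.** For two means, the detectable difference in SD units is d ≈ (1.960 + 0.842)·√(2/n). With n = 100 this is 2.802 × 0.1414 = 0.396; the two-sample t-test gives 0.398. Results from the t-test:

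| Analysed per arm | Assumed dropout | 80% power | 90% power |
|---|---|---|---|
| 100 | 0% | 0.40 SD | 0.46 SD |
| 90 | 10% | 0.42 SD | 0.49 SD |
| 80 | 20% | 0.45 SD | 0.52 SD |

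**4. What a zero-threshold responder would pick up by chance.** With no true change and symmetric error, the share scoring higher is f = (1 − t)/2, where t is the share with exactly zero change.

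- t = 0%: f = 50%
- t = 10%: f = 45%
- t = 20%: f = 40%
- t = 40%: f = 30%

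If every genuine improver registers as positive, the observed rate is q + (1 − q)f, where q is the share genuinely improved. For genuine rates of 0% and 20%, the observed difference is 0.20(1 − f):

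- f = 0.30: 30% vs 44%, 14 points, power 54% at 100 per arm.
- f = 0.50: 50% vs 60%, 10 points, power 29% at 100 per arm.

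**The case against.** The strongest reply is that the sample-size paragraph is planning shorthand. Its several loose terms are not offered as an endpoint definition, and since no between-arm analysis uses the proportion, noise in it biases no planned result. This stands. What can be said is that the responder is undefined, not that the plan has adopted a zero cut-off.

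Three stronger readings are tempting, and the documents do not support them.

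- A reader might infer that about half of unchanged patients would be counted as improved. That is the upper end of an assumed range. The plan gives neither the SF-12 measurement error nor the share of exact ties.
- A reader might infer that a 30% control rate requires either 40% exact ties or a worsening control mean. That holds for symmetric or normal change (for normal change, a mean of −0.52 SD of change), but not in general. If 70% fall by 3 points and 30% rise by 8, there are no ties, 30% improve, and the mean change is 0.30 × 8 − 0.70 × 3 = +0.3.
- A reader might infer that the score analysis is less sensitive than the stated threshold. If change is normal with a common SD, 30% vs 50% corresponds to a shift of 0.52 SD of change, above the 0.40 SD in the working. Only 30% vs 40%, about 0.27 SD, falls short, and that reflects the separate 20% versus 30%/40% conflict.

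It would also be too strong to say that improvement is never to be examined. The plan foresees exploratory work on predictors of improvement, although it specifies no method.

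**Conclusion.** The point holds as a mismatch between the endpoint used for sizing and the endpoint analysed. The sensitivity statement concerns an undefined binary outcome with no specified between-arm test, so it cannot be used to judge the primary HRQoL result. The planned score analysis is not invalid for this reason, and the mismatch alone does not show that it is underpowered.

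The size, on a simple two-mean basis at two-sided 5%, is a detectable difference of about 0.40 SD at 80% power with no dropout, and about 0.42 to 0.45 SD with 10% to 20% dropout. The dropout rates are assumptions. The mixed model's own sensitivity could differ, depending on the correlation between visits and on how baseline is handled, and the plan gives neither. Whether 0.40 SD is a worthwhile difference cannot be judged from the documents.

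The chance-responder rate of roughly 30% to 50% is conditional on symmetric error and 40% to 0% exact ties. It matters only if a responder analysis is carried out with no minimum change.

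**What to change.** Replace the responder sentence under Sample Size Determination with a statement for the planned score analysis, for example:

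> For the SF-12 [named score] at day 90, 100 per arm gives 80% power (two-sided 5%) for a between-group difference of about 0.40 SD with no dropout, or about 0.42 to 0.45 SD with 10% to 20% dropout (assumed), using a simple two-mean comparison as an approximation to the mixed model.

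Name the same score and the day-90 contrast under Primary Outcomes. If the sponsor has an SD for that score, add the difference in points so that its relevance can be judged.

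If a responder analysis is kept, including the exploratory work on predictors of improvement, state in advance its score, minimum change, time point and test. Dropping it or defining it are both acceptable. Use the same rewrite to remove the conflict between the 20% threshold and the 30% and 40% rates.

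The cost is a few sentences, with no extra patients or data. The downside is a threshold in SD units, which is less intuitive than a percentage.
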